16.2 Trial Documentation and Storage

The investigator must maintain a list of appropriately qualified persons to whom he/she has delegated trial duties. All persons authorized to make entries in and/or corrections to CRFs will be included on the delegation log.

Source documents are original documents, data and records containing all protocol-specified information from which the patient's CRF data are obtained. These include, but are not limited to, hospital records, clinical and office charts, laboratory and pharmacy records, diaries, microfiches, radiographs and correspondence. The source for each data point will be agreed with each center prior to patient recruitment. In the rare situations of data being recorded directly into the CRF in error, then the source data from the CRF should be transcribed into the patient's notes with appropriate signature and date to provide a full audit trail.

The investigator and trial staff are responsible for maintaining a comprehensive and centralized filing system of all trial-related, essential documentation (as outlined in the ICH Tripartite Guidelines for GCP Topic R6[R1]²⁶, Section 8.2), suitable for inspection at any time by representatives from GW and/or applicable regulatory authorities. Elements should include:

- Patient files containing completed CRFs, ICF forms and supporting copies of source documentation.
- Trial files containing the protocol with all amendments, IB, copies of pre-trial documentation (see Section 15.4) and all correspondence to and from the IRB/EC and GW.
- Enrollment log of all patients who consented to take part in the trial.
- Screening and recruitment log of all patients screened and whether or not they were recruited into the trial (i.e., randomized and/or dosed with IMP).

• Proof of receipt, IMP accountability record, return of IMP for destruction, final IMP reconciliation statement and all drug-related correspondence.

In addition, all original source documents supporting entries in the eCRFs, and diary data must be maintained and be readily available.

Following completion or termination of a clinical trial, GW will initiate proper archive of clinical trial-related documentation and electronic records generated by the investigator and/or GW. All clinical trial-related documents and electronic records will be retained within an archiving system for a period dependent upon need and for a minimum of 25 years. Essential documents must be retained until at least 2 years after the last approval of a marketing application in an ICH region and until there are no pending or contemplated marketing applications in an ICH region, or until at least 2 years have elapsed since the formal discontinuation of clinical development of the IMP. These documents must be retained for a longer period, however, if required by the applicable regulatory requirements³¹ or if needed by GW.

GW will inform the investigators for each center in writing of the need for record retention. No trial document may be destroyed without prior written agreement between GW and the investigator. Should the investigator wish to assign the trial records to another party or move them to another location, he/she must notify GW in writing of the new responsible person and/or the new location.

16.3 Trial Monitoring and Data Collection

The GW representative and regulatory authority inspectors are responsible for contacting and visiting the investigator for the purpose of inspecting the facilities and, upon request, inspecting the various records of the trial, e.g., CRFs and other pertinent data, provided that patient confidentiality is respected.

The GW trial monitor, or designee, is responsible for inspecting (on site or remotely) the CRFs and available diary data at regular intervals throughout the trial to verify adherence to the protocol, completeness, accuracy and consistency of the data and adherence to local regulations on the conduct of clinical research. The trial monitor must have (direct or remote) access to patient medical records and other trial-related records needed to verify the entries on the CRFs.

The investigator agrees to cooperate with the trial monitor to ensure that any problems detected in the course of these monitoring visits are resolved.

To ensure the quality of clinical data across all patients and centers, a clinical data management review will be performed on patient data received at GW or a CRO. During this review, patient data will be checked for consistency, omissions and any apparent discrepancies. In addition, the data will be reviewed for adherence to the protocol and FDA regulations^{27,28,29,39}, ICH Tripartite

Guidelines for GCP Topic $E6(R1)^{26}$ and all other applicable regulatory requirements. To resolve any questions arising from the clinical data management review process, data queries and/or center notifications will be sent to the center for completion and then returned to GW or the CRO, as applicable.

16.4 Quality Assurance

In accordance with the FDA regulations^{27,28,29}, EU Clinical Trials Directive³⁰/ICH Tripartite Guidelines for GCP Topic $E6(R1)^{26}$ and the sponsor's audit plans, representatives from GW's Clinical Quality Assurance Department may select this trial for audit. Inspection of center facilities, e.g., pharmacy, drug storage areas, laboratories, and review of trial-related records will occur to evaluate the trial conduct and compliance with the protocol, the EU Clinical Trials Directive³⁰/ICH Tripartite Guidelines for GCP Topic $E6(R1)^{26}$ and applicable regulatory requirements.

16.5 Compensation

GW will indemnify the investigator and the trial center in the event of any claim in respect of personal injury arising due to a patient's involvement in the trial, providing that the trial protocol has been adhered to. This would include claims arising out of or relating to the administration of the IMP or any clinical intervention or procedure provided for or required by the protocol to which the clinical trial patient would not otherwise have been exposed, providing there is no evidence of negligence on behalf of the investigator or their team. GW will not be liable for any claims arising from negligence on the part of the investigator or their team.

16.6 Publication Policy

GW recognizes that there is a responsibility under the regulatory guidelines to ensure that results of scientific interest arising from this clinical trial are appropriately published and disseminated. They will coordinate this dissemination and may solicit input and assistance from the chief/principal investigators. A summary of the results of this trial will be made available on http://www.clinicaltrials.gov and http://www.clinicaltrialsregister.eu/ (as applicable), as required by US and EU Law.

The raw data from this trial may be obtained by the PIs or by their steering committee representatives on request. Should they wish, PIs are allowed to conduct their own analyses and are permitted to present such information along with methods and results of the clinical trial at symposia, national or regional professional meetings and to publish it in theses or dissertations.

All publications, e.g., manuscripts, abstracts, oral/slide presentations or book chapters based on this trial, must be submitted to the GW Medical Affairs Department and, as applicable, GW Publication Committee for corporate review before release. To ensure adequate time for GW to make comments and suggestions where pertinent, all such material should be submitted to them at least 60 days prior to the date for submission for publication, public dissemination, or review by a publication committee. The PIs must then incorporate all reasonable comments made by GW into the publication.

GW also reserves the right to delay the submission of such information by a period of up to 6 months from the date of first submission to them in order to allow them to take steps to protect proprietary information where applicable.

16.7 Intellectual Property Rights

All intellectual property rights owned by or licensed to either GW or the PIs, other than those arising from the clinical trial, will remain their property. All intellectual property rights arising out of the clinical trial will vest in or be exclusively licensed to GW and, as such, the PI must promptly disclose all knowledge to GW and refrain from using such knowledge without the prior written consent of GW.

16.8 Confidential Information

GW and the PI must ensure that only personnel directly concerned with the trial are party to confidential information and that any information coming to either party about the other during the course of the trial must be kept strictly confidential and must not be disclosed to any third party or made use of without the prior written consent of the other.

APPENDIX 1 SCHEDULE OF ASSESSMENTS

Schedule of Assessments

Period	Screening			Treat	tment Peri	po			End of Taper	Follow-up ⁿ
Visit	Visit 1 ^a	Visit 2	Visit 3	Visit 4	Visit 5	Visit 6	Visits 7	Visit 8 EoT/WD	Visit 9	Visit 10
Visit Type	Clinic	Clinic	Telephone	Telephone	Clinic or Video Call and Home	Telephone	Clinic or Video Call	Clinic	Clinic or Video Call and Home	Telephone
Day	-14 to -7	1	7 (± 3)	14 (± 3)	Nurse 29 (± 3)	43 (± 3)	57 (± 3)	85 (± 3)	$\frac{\text{Nurse}}{\text{V8}+7}$	V9 + 14 (+ 3)
Informed consent/assent	Х						Ì			
Demographics	x									
Medical history ^b	Х									
Inclusion and exclusion criteria	X	Х								
AE review	Х	Х	Х	Х	Х	Х	Х	Х	Х	Х
SAE review	Х	Х	Х	Х	Х	Х	Х	Х	Х	Х
Concomitant medication review ^c	Х	Х	Х	Х	Х	Х	Х	Х	Х	Х
Test for drugs of abuse	x									
C-SSRS	Х	Х			Х		Х	Х	Х	
Vital signs ^d	Х	Х			Х			Х	Х	
Full physical examination	Х							Х		
Height	Х									
Weight	Х							Х		
BMI	Х									
12-lead ECG ^e	Х							Х		
Safety laboratory assessments $^{\rm f}$	Х				Х			If not tapering	Х	
Urinalysis ^g	х							If not tapering	х	

Page 84 of 88

V1, 24Sep15

dy Code: GWND19189	0 Number: 150775	tocol Version 2.0, 24 Nov 2020	
Study (ÍND N	Protoco	

|--|

Period	Screening			Treat	tment Peri	po			End of Taper	Follow-up ⁿ
Visit	Visit 1 ^a	Visit 2	Visit 3	Visit 4	Visit 5	Visit 6	Visits 7	Visit 8 EoT/WD	Visit 9	Visit 10
Visit Type	Clinic	Clinic	Telephone	Telephone	Clinic or Video Call and Home Nurse	Telephone	Clinic or Video Call	Clinic	Clinic or Video Call and Home Nurse	Telephone
Serum pregnancy test (WOCBP only)	Х							If not tapering	Х	
Trial treatment		Х	Х	Х	Х	Х	Х	Х	Х	
Randomization ⁱ		Х								
WASI-II (if required) ¹	Х									
ADOS-2 (if required)	х									
ABC ^j	Х	Х			х		Х	Х		
Vineland-3 ^{j,k}		Х			Х		Х	Х		
cGI-S ^k	Х	х			x		Х	X		
CGI-I ^k					Х		Х	Х		
IMP dispensing ^m		Х			Х			Х		
IMP review					Х			Х	Х	
Dosing diary completion (daily)					Х					
IMP dosing compliance review ^o			Х	Х	Х	Х		Χ	Х	
Abbreviations: ABC = Aberrant Beh;	avior Checklis	st: ADOS-2	= Autism Dia	apnostic Obser	vational So	chedule; AE =	adverse e	vents;		100
S - Clinical Global Immedian Series		- Columbio	Cuinide Cerre	rity Dating Co	olo. DCM	$- D_{incentrative}$	Ullucion Chatic	obal impress	tion improv 1 of Mantal	ement; cui- Disordars
5 - Current Orovan unpression Sever5th Edition; ECG = 12-lead electroca	ardiogram; Eo	$\Gamma = End of$	Treatment; IN	110 = investigation	tional medi	icinal product	accountab	sucal vialua ility;		

Page 85 of 88

RTSM = Randomization and Trial Management System; SAE = serious adverse events; WASI-II = Wechsler Abbreviated Scale of Intelligence Scale Second Edition; WD = withdrawal; WOCBP = women of childbearing potential.

- For visits carried out remotely, home nurse assessments include: collection of blood and urine samples (including urine dipstick), and vital signs.
- ^a Screening procedures may be performed over 2 days, if needed; both days must fall within the -14 to -7 day window.
- entry into the trial, and information on ASD history, including known etiologies. Patient has a diagnosis of ASD as per DSM-5 criteria for ASD, confirmed ^b Relevant, significant medical history will be obtained and is defined as any condition or disease that may affect the condition under study, is ongoing on by ADOS-2 criteria (conducted within 2 years at the trial site or at screening).
- All current and recent medication/therapy, i.e., taken within 14 days prior to the initial screening visit. All medications and interventions for ASD related symptoms must remain at stable doses throughout the trial; however, doses may be changed in response to a safety concern.
 - ^d Includes body temperature, pulse rate, and respiration rate and blood pressure taken in a sitting position at rest for 5 minutes.
- ^e Performed after 5 minutes in a supine position and reviewed by a physician.
- AST > 3 × ULN). If the patient in not tapering (and therefore will not attend Visit 9), clinical laboratory sampling is to be carried out at Visit 8. Details are f Includes hematology and biochemistry (including liver chemistries). Coagulation only at Visit 1; thereafter only as an unscheduled assessment if ALT or provided in Table 9.1-1.
- ^g Urinalysis to be performed provided urine can be obtained. Urine samples for biochemistry will be analyzed at the trial site (or by the home nurse) by use of a dipstick with any relevant findings being sent for further urinalysis at the central laboratory (urinalysis, microscopy, culture and sensitivity, as applicable) Details are provided in Table 9.1-1.
- previous IMP dose, and time and type of meal (snack, standard meal, high fat) consumed by the patient closest to the previous IMP dose will be collected. ^h The sample must be collected 12 hours (-3/+6 hours) since last IMP dose and before the patient's next dose. The time of sample collection, the time of To minimize discomfort samples should be collected together with the safety laboratory sample collection.
 - ¹ The RTSM system will be used to assign patients to treatment arms, including randomization.
- ¹ Caregivers questionnaires are to be completed by an identified main caregiver (nominated at Visit 1. The same identified caregiver is to complete the clinical interviews (Vineland-3 and
- ^k Investigator questionnaires/interviews are to be completed for each patient by the same investigator (CGI-S, CGI-I, Vineland-3, and
- should be performed prior to any invasive assessments being carried out. All assessments should reflect the patient's regular state; therefore, it should be ensured the patient had adequate time to settle prior to each assessment. WASI-II required if score within 1 year of screening is not available. ADOS-2 required if not performed at the trial site within 2 years. During special circumstances (e.g., COVID-19 pandemic) where the ADOS-2 cannot be performed due to site restrictions (e.g., mandatory use of face masks), eligibility can be confirmed using the Autism Diagnostic Interview, Revised (ADI-R). Patients functional assessments, i.e., the WASI-II, ADOS-2,
 - ^{III} In cases where Visits 5, or 9 are carried out at home, secure IMP delivery and collection will be organized
- ¹¹ If the patient did not enter the Taper Period, then Safety Follow-up occurs 14 days after Visit 8.
- ^o Dosing diary (completion and volumes taken) and time of IMP taken in relation to food will be reviewed

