4 EXPERIMENTAL PLAN

4.1 Trial Design

This is an exploratory, Phase 2, double-blind, randomized, placebo-controlled, multisite trial, which will compare the safety and efficacy of a 10/mg/kg/day dose of GWP42003-P versus placebo in children and adolescents with ASD.

Patients will be screened and if they meet eligibility criteria will be randomized to receive GWP42003-P or matching placebo in a 1:1 ratio. Patients will be stratified based on their age (6 to 11, 12 to 17), use of antipsychotics (on versus off), and region (North America versus Rest of the World). Patients will be administered 5 mg/kg/day GWP42003-P or matching volumes of placebo for 1 week and then 10 mg/kg/day GWP42003-P or matching volumes of placebo for 1 weeks. At the end of treatment, patients will taper the medication over 1 week.

A schematic (Figure 1-1), presented at the end of Section 1, depicts the overall trial design. More detailed information on treatment and trial procedures is provided in Section 8 and Section 9, respectively.

Eligible patients may be randomized 7 to 14 days after the screening visit (Visit 1), once all required assessments have been completed and laboratory results have been reviewed; if required, screening assessment may be spilt over 2 visits; however both visits must fall into the 7 to 14 day window prior to randomization (Visit 2). One week and 2 weeks following randomization, there will be 2 safety telephone visits (Visit 3 and 4). The patient will return to the clinic or video call and home nurse visit, 4 weeks after randomization (Visit 5). Six weeks after randomization, there will be another safety call (Visit 6), and then the patient will return for a clinic visit or video call visit (Visit 7) 8 weeks after randomization. The end of treatment visit will take place 12 weeks after randomization (Visit 8). If at any point it is decided to withdraw a patient from the trial, the patient should return to the clinic as soon as possible and complete Visit 8 procedures. At Visit 8, patients will commence to taper the medication (unless in case of withdrawal the medication was already discontinued or continued dosing is inadvisable, e.g., due to an AE). At the end of taper, the patient will return to the clinic or video call and home nurse visit (Visit 9). All patients will have a follow-up safety telephone visit, 14 days after Visit 9 or Visit 8 (in case the patient did not taper the medication).

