Visit windows are allowed as defined in the schedule of assessment. Visit 3, 4, 5, 6, 7, and 8 days and windows are counted from the day of randomization (Visit 2). Visit 9 day and window is counted from the day of Visit 8. Visit 10 day and window is counted from the day of Visit 9, or the day of Visit 8 (if the patient did not enter the taper period).

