8.1.2 Dose Escalation, Adjustments, and Taper

Patients will be administered 5 mg/kg/day GWP42003-P or matching volumes of placebo for 1 week and then 10 mg/kg/day GWP42003-P or matching volumes of placebo for 11 weeks.

If an unacceptable AE develops at any time during the dose escalation or treatment periods, dosing should be reduced, at the investigator's discretion and in a blinded manner, until the event has resolved or is well tolerated. The end of treatment taper schedule should be used to guide dose adjustment. If required, dosing may be suspended. Patients whose dose has been decreased should have their dose increased again, if the tolerability improves. Patients unable to tolerate the target dose may stay at a lower dose. If a patient cannot tolerate a dose of 5 mg/kg/day, the investigator should discuss with the medical monitor whether patient continuation in the trial is recommended. Single dose volumes must be at least 0.1 mL.

Transaminase elevations should be medically managed by the investigator either by reducing the IMP dose or, following discussion with the medical monitor, by reducing concomitant medications judged to be causing the elevation (as per Section 10). For potential cases of drug-induced liver injury see Section 12.9.

Dose adjustments should be discussed with the GW medical monitor. The final decision regarding dose adjustments should be taken by the investigator.

At the end of treatment, patients will taper the medication in steps of -2.5 mg/kg/day every 2 days.

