13.6.3.3 Clinical Laboratory Data

Clinical laboratory data will be summarized at screening, baseline, and at each time point during the treatment period using appropriate summary statistics. Categorical shift tables will be presented, showing the numbers of patients with values outside the normal range. Change from baseline will also be summarized by visit.

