8.1 Exposure and treatment compliance

Exposure

Exposure to GWP42003-P or placebo will be summarized using the following parameters:

- Treatment duration, calculated as the number of days subject received study drug, using the formula:
 - (the date of the last dose the date of the first dose +1). [CFR data]
 - Treatment duration will be summarized overall and separately for treatment and taper period.
- Average dose (mg/kg/day) based on diary reported days by visit and overall

Diary compliance

Diary compliance (%) is calculated by:

Diary entries * 100/ expected diary entries.

Expected diary entries are derived from treatment duration.

Dose compliance based on Diary

Number of doses administered, as reported in the diary, and dose compliance percentage will be summarized overall and separately for treatment and taper period

Dose compliance based on Diary (%) is calculated by:

Number of doses administered * 100/ number of diary entries (am+pm)

Dose compliance based on CRF

Total expected volume since last dispensation, total volume actually taken since last dispensation and derived dose compliance (%) are captured on CRF at Visit 5, Visit 8 EoT/WD, and Visit 9/End of Taper; derived dose compliance will be summarized for each period.

Number and percentage of subjects compliant will be summarized for each period by treatment group and overall for following groups;

Compliant: ≥75% to ≤125%

Minor Compliance Deviations 50-75 & 125-50 Major Compliance deviations: <50 and >150

Consistency of dose administration in relation to meal timing (Yes, No) by visit will be summarized separately.

Dose adjustment and suspension

The number and percent of subjects with any dose adjustment (overall and by reason) as collected on Investigator Dose Adjustment CRF will be summarized.

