8.3 Clinical Laboratory Results

Laboratory tests will include hematology, serum biochemistry, coagulation (Visit 1 only; thereafter only as an unscheduled assessment if ALT or AST > 3 x ULN), Clinical laboratory sample parameters are detailed in Table 9.1-1 in the study protocol. Urinary data and the drug abuse data will only be listed.

In case of values <LLoQ or >ULoQ, LLoQ or ULoQ, respectively, will be used in summary tables.

All test results and abnormal laboratory values will be presented in data listings.

Summaries of actual values and changes from baseline for numeric test results will be presented for each assessment time point.

Shift tables will be summarizing the counts and percentages of subject's baseline CTCAE grade versus worst CTCAE grade at any postbaseline visit.

Potential Cases of Drug-Induced Liver Injury

A table will summarize the number of subjects by the following criteria.

At baseline:

- ALT > 1 x ULN
- AST > 1 x ULN
- ALT or AST > 1 x ULN
- TBIL > 1 x ULN
- ALT or AST or TBIL > 1 x ULN

At any time point after first dose of study treatment:

- ALT > N x ULN, where N=1, 2, 3, 5, 8
- AST > N x ULN, where N=1, 2, 3, 5, 8
- ALT or AST > N x ULN, where N=1, 2, 3, 5, 8
- ALP > 2 x ULN
- TBIL > 1 x ULN
- TBIL > 2 x ULN
- ALT or AST > 3 x ULN and TBIL > 2 x ULN
- ALT or AST>3 x ULN and INR > 1.5

The summary table will be done by sex,

and

overall.

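### Do the SAP's laboratory tables mislead because tapering patients have no scheduled panel between Day 29 and the end of taper?

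*Protocol*

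**What the plan says.** The safety laboratory row of Protocol Appendix 1 is marked at Visit 1, Visit 5 (Day 29 ± 3) and Visit 9 (seven days after Visit 8). The Visit 8 cell reads "If not tapering", and footnote f explains it: "If the patient in not tapering (and therefore will not attend Visit 9), clinical laboratory sampling is to be carried out at Visit 8". No panel is scheduled at Visits 6 or 7.

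Protocol 4.1 makes tapering the default: "At Visit 8, patients will commence to taper the medication (unless in case of withdrawal the medication was already discontinued", or unless further dosing is judged inadvisable. The taper itself is in Protocol 8.1.2: "At the end of treatment, patients will taper the medication in steps of -2.5 mg/kg/day every 2 days".

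On reporting, Protocol 13.6.3.3 states: "Clinical laboratory data will be summarized at screening, baseline, and at each time point during the treatment period using appropriate summary statistics". SAP 8.3 states: "Summaries of actual values and changes from baseline for numeric test results will be presented for each assessment time point". SAP 8.3 also tabulates liver thresholds over all samples after the first dose, and shifts to the worst post-baseline grade. Neither is divided by dosing state. For exposure, by contrast, SAP 8.1 says: "Treatment duration will be summarized overall and separately for treatment and taper period".

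SAP 4.4 uses nominal visits, moves early-withdrawal data to the nearest scheduled visit, and lets unscheduled values into worst-case summaries but not into by-visit rows.

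**The concern.** Laboratory parameters are a safety endpoint, and Protocol 3.2 names hepatocellular injury as an important expected risk. Two outputs look unsafe to read at face value.

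First, a by-arm Visit 8 laboratory row would contain only patients who did not taper. Under Protocol 4.1 these are mainly patients who had already stopped drug at withdrawal, or who should not continue, for example because of an adverse event. That group is selected on events after randomisation, so comparing arms within it is not a randomised comparison.

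Second, the liver table combines samples taken at target dose with samples taken at or near the end of taper. A low count could be taken as evidence from 11 weeks of scheduled monitoring at target dose, when the last scheduled target-dose panel for most patients is at Day 29. Since SAP 8.1 separates treatment from taper for exposure, its absence in SAP 8.3 looks like an oversight.

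**Working it through.** **Interval between panels (Appendix 1).** Visit 5 is Day 29, Visit 8 is Day 85, and Visit 9 is 85 + 7 = Day 92.
- Nominal interval: 92 − 29 = 63 days.
- With the ±3-day windows on Visits 5 and 8: shortest (82 + 7) − 32 = 57, longest (88 + 7) − 26 = 69.
- Protocol 4.1 says "Visit 9 day and window is counted from the day of Visit 8", but no width for Visit 9 is legible in the schedule. If it were ±3 days (an assumption), the range would be (82 + 4) − 32 = 54 to (88 + 10) − 26 = 72. The special-circumstances extension in Protocol 9.2 could widen it further.

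**Target-dose time after the Day 29 panel.** One week at 5 mg/kg/day and then 11 weeks at 10 mg/kg/day puts target dose on Days 8 to 84, which is 77 days. Days 30 to 84 are 55 days; 55/77 = 71%. Counting Day 29 itself gives 56/77 = 73%. Both apply to patients who stay at target dose.

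**Dose at the Visit 9 sample.** Apply the written steps from 10 mg/kg/day.
- First step on the day of Visit 8: 7.5, 5 and 2.5 for two days each, then 0 from V8+6, so 0 at V8+7.
- First step at V8+2: 2.5 on V8+6 and V8+7, so 2.5 at V8+7.

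The Visit 9 panel is thus an end-of-taper sample, as its heading in Appendix 1 says.

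**Size of the Visit 8 row.** The documents give no figure. Protocol 13.1 plans for 10% drop-out: 144/(1 − 0.10) = 160, which reproduces the stated number randomised. The implied non-completers are 160 − 144 = 16 over both arms. If every completer tapers (an assumption), the row holds between 0 and about 16 patients, against about 144 at Visit 9. Withdrawing patients who taper would lower it; completers who do not taper would raise it.

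**Effect of SAP 4.4.** Its mapping rule has two readings for laboratory data. If any scheduled visit counts, a withdrawal between Visits 5 and 7 maps to Visit 6 or 7, where no panel is scheduled. If only visits with that assessment count, it maps to Visit 8. No number of mapped patients or days can be fixed from the text. Neither reading puts a tapering completer's scheduled sample into the Visit 8 row.

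**What the tables would show.**
- By-visit summaries: Visit 5 (target dose) and Visit 9 (end of taper) are separate rows. The Visit 8 row carries its own n.
- Liver thresholds and worst-grade shifts: any post-dose value counts, including unscheduled ones.
- Adverse events (SAP 8.2): tabulated by time of first onset, with a cut at 12 weeks. Since 12 × 7 = 84 days after Day 1 is Day 85, the cut falls at nominal Visit 8. Laboratory results judged to be adverse events (Protocol 9.1.9) therefore already get an approximate treatment/taper split.
- Listings: all laboratory results.

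**The case for a change.** The strongest case for acting is that it would be cheap. A label on the Visit 8 row, a split liver table and a count of patients with a later on-treatment panel need no new data, and they would show how little scheduled target-dose coverage exists after Day 29. SAP 8.9 states the non-tapering condition for pregnancy tests, so SAP 8.3 could do so for laboratory tests. Read literally, Protocol 13.6.3.3 would also leave out Visit 9, the only late scheduled panel for tapering patients.

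The facts behind this stand; the gain is small. A before/after-taper split has no place for patients who never taper, whose samples may be off drug and would fall in with target-dose values. A count of panels after Day 29 would include ordinary Visit 5 panels drawn in window on Days 30 to 32. A sound version needs three dosing states (on treatment, taper, off drug) and would spread small counts thinly. The wording difference resolves itself: Protocol 13 leaves analysis detail to the SAP, and the SAP's broader phrase keeps Visit 9. The any-time liver table largely follows the criteria in Protocol 12.8, which apply to any patient after randomisation, and neither document presents it as continuous coverage at target dose.

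**Conclusion.** No change follows. The schedule is internally consistent, and SAP 8.3 can be carried out as written. The result is a small descriptive Visit 8 row with n shown, separate Visit 5 and Visit 9 rows, and a conventional worst-case liver table. Both arms follow the same schedule, no hypothesis test is attached to the laboratory data, and no efficacy result is touched. An analyst preparing the displays would sensibly footnote Visit 8 as non-tapering patients; the separate TLF shells document, which was not available, may already do so.

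The interpretive caution remains: for tapering patients the any-time liver counts rest on scheduled panels nominally 63 days apart (57 to 69 with the Visit 5 and 8 windows), plus whatever unscheduled tests were done. That is visible from Appendix 1 and the by-visit rows. The figure of about 16 patients is an illustration from planned drop-out, and the 71% assumes patients stay at target dose. Whether the sampling schedule itself is adequate is for the sponsor's clinicians.
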